### 7.17 ACUTE GVHD DIAGNOSIS

GVHD diagnosis will be confirmed by biopsies of organs involved per the institutional standards, when the clinical features are consistent with GVHD. The diagnosis and biopsy results must be confirmed by the PI on the source documents and entered into the eCRF.

### 7.18 ACUTE GVHD CLINICAL GRADING AND STAGING

Acute GVHD grading and staging will be performed by the Investigator as per procedures described in the Technical Manual of Procedures version 3.0 and dated 19 March 2013 (Blood and Marrow Transplant Clinical Trials Network):

- Assessment of the clinical acute GVHD using the form Clinical Acute GHVD (see Figure 7-2);
- Assessment of the GVHD staging using the GVHD Staging table (see Table 7-2);
- Assessment of the GVHD grading using the GVHD Grading Scale (see Table 7-3);
- Assessment of the GHVD index using the CIBMTR GHVD Index (see Table 7-4).

Figure 7-2: Clinical Acute GVHD Assessment

DatePatient ID _				K	arnofsl	cy/Lansk	ιу	
Code			Drug	Cond	Diagno			7247
0 1 2 3 Skin	4 5   % body rash:		Rxn	Reg	TPN	Infect	VOD	Other
					_		85	
Lower GI	□ □ Vol:						100	
Upper GI 🔲 🔲								
Liver	Max bili:							
☐ Pentostatin		Pred Etanercep	ot		lethylpr ther		☐ Onta	ak
Pentostatin  Code Definitions:			ot				⊔ Onta	ak
Code Definitions:	☐ MMF ☐  Lower GI (Diarrhea):		ot	u	ther	l:	Liver (	Bilirubin):
Code Definitions: Skin: D No rash	☐ MMF ☐  Lower GI (Diarrhea):  0 None	Etanercep	ot	u 10	ther opper G	l: racted	Liver (	Bilirubin): mg/dl
Code Definitions:		Etanercep /m² 0- 555 mL	Jm²	U 10	ther	l: racted and	Liver () 0 <2.0 1 2.1-3	Bilirubin):
Code Definitions:  Skin:  0 No rash 1 Maculopapular rash, <25% of body surface 2 Maculopapular rash,	Lower GI (Diarrhea):  0 None 1 ≤500 mL/day or <280 mL 2 501-1000 mL/day or 28 3 1001-1500 mL/day or 5	Etanercep m  0- 555 mL 56- 833 m	Jm²	0 0 0 1 1 1	other	l: racted and g	Liver (0 < 2.0 1 2.1-3 2 3.1-3 6.1-	Bilirubin): mg/d1 3.0 mg/d1 6.0 mg/d1 15.0 mg/d
Code Definitions:  Skin:  No rash  Maculopapular rash, <25% of body surface		/m  0- 555 mL 56- 833 m mL/m 	Jm² L∕m²	0 0 0 1 1 1	other oper G No prot nausea vomitin	l: racted and g ent	Liver (0 < 2.0 1 2.1-3 2 3.1-3 6.1-	Bilirubin): mg/dl 3.0 mg/dl

CONFIDENTIAL Page 77 of 108

### 7.19 STANDARD INSTITUTIONAL PRACTICES FOR STEM CELL INFUSION

Procedures for selection of donors and stem cell dose will follow FDA requirements for Blood Products (21 CFR 640) and Human Cellular and Tissue Based Products (21 CFR 1271). The standard institutional practices for cell transplants will also be followed including the use of G-CSF, irradiations and infection prophylaxis. The inclusion criteria for peripheral blood stem cell (PBSC) donors are detailed in section 3.3.1 of this study.

The sources of stem cells to be used in this study will consist only of bone marrow and peripheral blood. The cord blood will be excluded as graft source to avoid confound incidence of GVHD. Minimum recommended doses for each of stem cells source will be as follows:

- Bone marrow: minimum of 2 x 10^6 CD34+ cells/kg of recipient's body weight;
- Peripheral blood: minimum of 2 x 10^6 CD34+ cells/kg of recipient's body weight.

# 7.19.1 Conditioning Regimen of Stem Cells

For the purpose of this study, only myeloablative conditioning regimens will be used. Total Body Irradiation (TBI) and chemotherapy conditioning regimens can be used in concordance with the clinical site's standard procedures. The clinical sites should use chemotherapy with or without TBI with the minimum cumulative dosages mentioned below:

- TBI at 1200 cGy;
- Cyclophosphamide at 120 mg/kg;
- Etoposide at 60 mg/kg;
- Melphalan at 100 mg/m^2;
- Busulfan at 12 mg/kg;
- Fludarabine at 160 mg/m2;
- In case that TBI is used with combination of Busulfan and fludarabine, the minimum dose of TBI will be 400 cGy.

CONFIDENTIAL Page 79 of 108

#### 8 STATISTICAL CONSIDERATIONS

This section presents general information about statistical considerations and concepts such as randomization, sample size, and a brief discussion on analysis methodology, as well as some data conventions. Detailed descriptions of the statistical analysis methods and data conventions that will be used in this study will be in a separate document; i.e., the Statistical Analysis Plan (SAP).

#### 8.1 TREATMENT GROUPS

This is a placebo-controlled study. The following treatment groups will be assessed:

Group	Description
Active Treatment	Standard GVHD prophylaxis + PRO140
Control Treatment	Standard GVHD prophylaxis + Placebo

#### 8.2 DESCRIPTION OF STUDY ENDPOINTS

## 8.2.1 Primary Efficacy Endpoint

Incidence of Grade II, Grade III or Grade IV acute GVHD by Day-100

## 8.2.2 Secondary Efficacy Endpoints

- Incidence of severe and life-threatening (Grade III and Grade IV) acute GVHD by Day 100
- Incidence of organ-specific acute GVHD by Day-100
- Effect of PRO 140 or Placebo on donor engraftment by T-cell and myeloid chimerism in peripheral blood
- Effect of PRO 140 or Placebo on neutrophil and platelet count recovery
- Changes in ECOG performance score
- GVHD-free survival (GFS)

## **8.2.3** Safety Assessments

- Tolerability of repeated subcutaneous administration of PRO 140 as assessed by study participants (using Visual Analogue Scale) and by investigator-evaluation of injection site reactions
- Frequency of treatment emergent adverse events and serious adverse events

CONFIDENTIAL Page 80 of 108

- AML or MDS relapse rate by Day-100
- Changes and shifts in laboratory measurements over time
- Changes in Electrocardiogram (ECG) parameters over time

#### 8.3 SAMPLE SIZE DETERMINATION AND RATIONALE

For this two arm clinical trial, it is planned to have a total of 60 subjects (30 per treatment group). The sample size is on the basis of clinical judgment and not based on statistical power calculation. The number of subjects was deemed adequate to provide clinically meaningful descriptive results consistent with study objectives.

## 8.4 RANDOMIZATION, STRATIFICATION AND BLINDING

This is a double-blind, multi-center randomized clinical trial. The randomization will be central and will use mixed blocks of 2 and 4 with a 1:1 ratio of Active to Control to ensure even distribution of Active and Control subjects.

Randomization will be conducted via a Web based system, and the process for the blinding requirements will be outlined in the study randomization plan. To decrease the effect of HLA-Matched Unrelated Donor (MUD) vs HLA-Mismatched Related Donor (MRD) as a confounding factor in this study, the donor source will be used as a stratification factor. This stratification will allows us to achieve a balanced randomization scheme with more reliable interpretation.

### 8.5 Interim Analysis

There will be a safety interim analysis after the first 10 subjects complete the treatment or withdraw from the study, whichever occurs first. The data from this interim analysis will be reviewed by an independent Data Monitoring Committee (DMC). The DMC responsibilities will be further elaborated in the study DMC charter.

There is no planned interim analysis for efficacy.

To protect the integrity of the blinded data, the IA will be conducted based on a Standard Operating Procedure for Interim Analysis that has a well-established firewall to protect the integrity of the trial. The details of the IA, including the below bullet points, are included in the Statistical Analysis Plan (SAP) for the study.

- The goals of the IA
- IA procedures for data preparation
- IA procedures for conduct of the analysis
- Data to be shared with the DMC

CONFIDENTIAL Page 81 of 108

- Information to be shared with the sponsor after the IA
- The stopping rule
- Protection of Type I error rate and adjustments

### 8.6 GENERAL STATISTICAL CONSIDERATIONS

## 8.6.1 Analysis Populations

### **8.6.1.1** Intent-to-Treat Population

The Intent-to-Treat (ITT) population is defined as the set of subjects who are randomized to PRO 140 or placebo. The ITT population will be the primary analysis population for the analysis of primary and secondary endpoints.

## 8.6.1.2 Per Protocol Population

The Per Protocol (PP) population is defined as the set of subjects who meet the ITT population requirements, and were not associated with a major protocol violation. This population will be identified before the database lock. The PP population will be the supportive analysis population for the analysis of primary and secondary endpoints.

## 8.6.1.3 Safety Population

The Safety population is defined as all subjects who received at least one dose of PRO 140 or placebo after randomization. This population will be used for the analysis of safety parameters.

### 8.6.2 Statistical Methods

All collected study data will be presented in subject data listings. Statistical analyses will be performed using SAS® for Windows, version 9.3 or later.

## **8.6.3** Prognostic Factors/Covariates

There are no pre-planned covariates analyses of the data from this study.

[figure not shown]
## 8.6.4 Handling of Missing Data

For the per-protocol analysis of efficacy endpoints there will be no imputation of missing data. However, missing data will be imputed using methods that will be detailed in the SAP for the ITT population of the primary and secondary endpoints.

### 8.7 DATA SUMMARY

A SAP will be developed and approved before the database is locked. The SAP will present the detailed statistical methodology to be used in analyzing the efficacy and safety data from this trial.

CONFIDENTIAL Page 82 of 108

All statistical tests will be 2-sided and a 0.05% significance level will be used throughout the analyses.

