2.2 Design Overview

This is a Phase II, randomized, double-blind, placebo-controlled, multi-center study to evaluate the feasibility of the use of PRO 140 as an add-on therapy to standard GVHD prophylaxis treatment for prevention of acute GVHD in adult patients with AML or MDS undergoing allogeneic HCT.

In this study, 60 subjects will be randomized to receive either PRO 140 or placebo in a 1:1 ratio (i.e. 30 subjects per arm). PRO 140 or placebo will be administered as a 350 mg subcutaneous injection on Day -3 or Day -2 prior to stem cell infusion, on the day of stem cell infusion (Day 0), and then weekly for 30 days (at Week 1, Week 2, Week 3 and Week 4) after which it will be administered every two weeks for up to 100±7 days (at Week 6, Week 8, Week 10, Week 12 and Week 14). Subjects will return to clinic for two Follow-up visits at 2 weeks after the last treatment visit, and one year after the first treatment visit.

The study will have three phases: Screening Phase, Treatment Phase and Follow-up Phase as shown in the study flow diagram Figure 2-1.

Figure 2-1 Clinical Trial Flow Diagram

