4. SAMPLE SIZE DETERMINATION AND RATIONALE, STATISTICAL POWER, AND SIGNIFICANCE LEVEL

For this two arm clinical trial, it is planned to have a total of 60 subjects (30 per treatment group). This is a proof of concept study, and sample size is on the basis of clinical judgment and not based on statistical power calculation. The number of subjects was deemed adequate to provide clinically meaningful descriptive results consistent with study objectives. Based on literature review, the incidence of GVHD in ablative transplant population range from 40-60%. Assuming that the control incidence of GVHD is 50% and that of the Active group is 15%, a sample size of 30 subjects per group produces a two-sided 95% CI for the difference in proportions with a width of 0.44 (i.e.,95% CI of 0.13 – 0.57).

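### Protocol 8.7 sets the significance level at 0.05% (0.0005), a hundred times stricter than the SAP's 95% planning interval implies, so the effect the SAP plans for would not be significant if observed

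*Protocol*

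**What the plan says.** The closing sentence of Protocol 8.7 (Data Summary) reads "All statistical tests will be 2-sided and a 0.05% significance level will be used throughout the analyses". It covers the primary comparison, for which Protocol 8.7.5.1 and SAP 8.2.1 prescribe a chi-square or Fisher's exact test, and the secondary efficacy tests in SAP 8.2.2.

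SAP section 4 is headed "SAMPLE SIZE DETERMINATION AND RATIONALE, STATISTICAL POWER, AND SIGNIFICANCE LEVEL" but states no significance level. It assumes GVHD incidences of 50% (control) and 15% (active) and reports that 30 subjects per group "produces a two-sided 95% CI for the difference in proportions with a width of 0.44", running from 0.13 to 0.57. It also says that the sample size rests on clinical judgment and not on a power calculation.

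Three SAP sections bear on whether a strict level could be deliberate. Section 5 plans no efficacy interim analysis, section 5.1.4 says the safety interim does not affect the Type I error rate, and section 7.6 makes no multiplicity adjustment.

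**The concern.** A level of 0.05% is 0.0005. A two-sided 95% interval corresponds to a two-sided test at 0.05. The level written for testing and the level used for planning therefore disagree, and the SAP states no significance level that would override the protocol.

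The level decides which between-group differences will be called significant. With 30 subjects per arm, the factor of 100 separates a threshold that a large effect would usually cross from one that it would usually miss. If the wording stands until the data are unblinded, any p-value between 0.0005 and 0.05 could be called significant or not, depending on whether the text is taken literally or as a slip.

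**Working it through.** **Inputs.** Control 50%, active 15% and a control range of 40% to 60% from the literature (SAP 4); 30 per arm (SAP 2.2); two-sided tests and alpha = 0.05% = 0.0005 (Protocol 8.7); chi-square or Fisher's exact test (SAP 8.2.1). Results are shown for both tests because the plan does not choose between them.

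**1. Reproduce the SAP's interval.** Wald interval with unpooled variance:

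SE = √(0.50×0.50/30 + 0.15×0.85/30) = √0.012583 = 0.1122

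0.35 ± 1.960 × 0.1122 = 0.130 to 0.570, width 0.440. This matches SAP section 4, so the planning calculation is sound and does use the 5% level.

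**2. Compare the two levels.** 0.05 / 0.0005 = 100. The critical value rises from 1.960 to 3.481. The interval that matches 0.0005 is a 99.95% interval: 0.35 ± 3.481 × 0.1122 = −0.04 to 0.74. It includes zero, whereas the 95% interval does not.

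**3. Test the planned result.** With a pooled proportion of 0.325, SE₀ = √(0.325×0.675×2/30) = 0.1209, z = 0.35/0.1209 = 2.89 and p = 0.0038. Since 15% of 30 is 4.5 events, the nearest whole-number tables are:

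| Control vs active events | Chi-square p | Fisher p | At 0.05 | At 0.0005 |
|---|---|---|---|---|
| 15/30 vs 4/30 | 0.0023 | 0.0048 | significant | not significant |
| 15/30 vs 5/30 | 0.0062 | 0.0127 | significant | not significant |

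**4. Find the active-arm count needed when control is 15/30.**
- At 0.05: at most 7 events by chi-square (p = 0.032) or at most 6 by Fisher (p = 0.029).
- At 0.0005: at most 2 events by either test (p = 0.0002 by chi-square, 0.0004 by Fisher). Three events already fail (p = 0.0007 and 0.0015). With the Yates correction the limit is 1 event, because 2 events give p = 0.0006.

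**5. Power if the planning rates are the true rates.** The documents state no power. The figures below come from enumerating all 31 × 31 outcomes for 30 per arm and summing the binomial probabilities of those with p at or below alpha. The active rate is 15% throughout.

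| Control rate | Chi-square, 0.05 | Fisher, 0.05 | Chi-square, 0.0005 | Fisher, 0.0005 |
|---|---|---|---|---|
| 40% | 60% | 49% | 8% | 5% |
| 50% | 85% | 78% | 27% | 21% |
| 60% | 97% | 94% | 57% | 49% |

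The normal approximation agrees at 50% versus 15%: power = Φ[(0.35 − z×0.1209)/0.1122], which is 84% for z = 1.960 and 26% for z = 3.481.

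**6. Sample size for 80% power at 50% versus 15%.** n per arm = [z_α√(2×0.325×0.675) + 0.842√(0.25 + 0.1275)]² / 0.35². This gives 27 at 0.05 and 66 at 0.0005 (33 and 71 with continuity correction). The planned 30 per arm is close to what a 5% test needs and less than half of what a 0.05% test needs.

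**The case against.** The strongest reply is that 0.05% is plainly a conflation of 0.05 and 5%. The protocol defers detailed methods to the SAP, and the only confidence level the SAP uses is 95%, so a statistician working from the SAP would be unlikely to apply 0.0005. That reading of the cause is probably right. It does not settle the matter, because the SAP states no significance level and the protocol figure remains the only one in force.

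A second reply is that this is a proof-of-concept study whose size was chosen for descriptive results. No success or go/no-go criterion is tied to a p-value, and the 50% versus 15% case illustrates precision; it is not a powered target. This is fair, and it limits what the power figures mean: they show how strict 0.0005 is and do not show a broken design commitment. Even so, efficacy against placebo is the primary objective and between-group tests are prespecified, so a level has to be stated and has to be the intended one.

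Two limits on the consequences also stand. If 50% and 15% are the true rates, roughly one trial in four or five would still reach 0.0005, so failure is likely but not certain. And the 95% interval appears only in the sample-size rationale. The planned efficacy analyses list no confidence interval for the difference, so a visible clash between p-value and interval would arise only if such an interval were reported.

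**Conclusion.** The concern holds. Protocol 8.7 sets a two-sided level of 0.0005 for all tests, neither document corrects or explains it, and it is 100 times smaller than the level behind the SAP's interval. If the observed rates are close to the planned ones (15/30 versus 4/30 or 5/30), the result passes 0.05 and fails 0.0005 under both named tests. If 50% and 15% are the true rates, 73% of trials (chi-square) or 79% (Fisher) would miss the written threshold, against 15% or 22% at 0.05.

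These sizes assume literal use of the protocol figure, 30 evaluable subjects per arm and the SAP's planning rates. Across the SAP's 40% to 60% control range, power at 0.0005 runs from 5% to 57% depending on the test. The inconsistency itself needs none of these assumptions. Because it concerns the threshold for the primary comparison and cannot be cleanly settled after unblinding, it must be fixed beforehand.

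**What to change.** In Protocol 8.7, replace the figure with a two-sided 5% (0.05) significance level. In SAP section 4, add one sentence stating the same level, so that the section delivers what its heading announces and agrees with the 95% interval already there. If 0.0005 was in fact intended, give the reason and restate the planning interval at the matching 99.95% level. Make the change before database lock and unblinding. The cost is one figure in the protocol and one sentence in the SAP, with no effect on trial operations or sample size.

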## 8.7.1 Subject Disposition

The disposition of all subjects who sign an ICF will be provided. The number of subjects screened, received treatment, completed, and discontinued during the study, as well as the reasons for all post treatment discontinuations will be summarized. Disposition and reason for study discontinuation will also be provided as a by-subject listing.

## 8.7.2 Demographic and Baseline Characteristics

Demographics and baseline characteristics (i.e., Age, Gender, HIV rapid antigen test, etc.) will be summarized using appropriate descriptive statistics.

Medical history of the subjects will also be provided as a by-subject listing and included as a baseline characteristic.

### 8.7.3 Prior and Concomitant Medications

Prior and concomitant medications will be summarized for the Safety population. All prior and concomitant medications recorded in the CRFs will be coded to matching Anatomic Therapeutic Classification (ATC) codes using World health Organization (WHO) drug dictionary. Summaries will be prepared using the coded terms. All prior and concomitant medications recorded in the eCRFs will also be listed.

## 8.7.4 Administration of Study Drug

All the data from administration of study drug will be summarized and/or listed appropriately.

CONFIDENTIAL Page 83 of 108

## 8.7.5 Efficacy Analysis

# 8.7.5.1 Primary Analysis

The primary analysis will be conducted on the ITT population.

The primary efficacy endpoint for this study is the incidence of  $\geq$  Grade II acute GVHD by Day - 100.

Chi-square/ Fisher's exact test will be used to compare the primary endpoint between the treatment groups.

All data from the secondary endpoints will be summarized and tabulated according to the variable type:

- Continuous data summaries will include:
  - O Descriptive statistics (n, mean, standard deviation, median, minimum and maximum) will be presented by treatment group
  - o For inferential statistics, if the Normality assumption is met, t-test will be used and if the Normality assumption is not met, a non-parametric method will be used.
- Categorical data summaries
  - o Frequencies and percentages will be presented by treatment group.
  - o For inferential statistics Chi-square or fisher's exact test will be used.

## 8.7.5.2 Supportive Analysis

To assess the consistency of the Primary Analysis results, supportive analysis will be conducted using the Per Protocol (PP) population. Statistical methodology for the supportive analyses will be the same as that of the primary analysis, with the exception of the analysis population used.

### 8.7.6 Safety Analysis

The Safety population will be used for the analysis of safety assessments.

For continuous variables data will be summarized using n, mean, Standard Deviation (SD), minimum and maximum values. For categorical variables data will be summarized using frequency and percentage. No inferential statistics are planned.

### 8.7.6.1 Adverse Events

Adverse events will be coded using Medical Dictionary for Regulatory Activities (MedDRA). TEAEs are defined as events with an onset on or after the first treatment. TEAEs will be summarized by treatment group, System Organ Class, and preferred term. The following TEAE summaries will be provided:

CONFIDENTIAL Page 84 of 108

- Overall TEAEs
- TEAEs by severity grade
- TEAEs by relationship to study treatment.

In addition, separate summaries of SAEs, and AEs resulting in discontinuation of study treatment will be presented.

## 8.7.6.2 Tolerability Assessment

All data from tolerability assessments of repeated subcutaneous administration of PRO 140 as assessed by study participants (using Visual Analogue Scale) and by investigator-evaluation of injection site reactions will be summarized.

## 8.7.6.3 Clinical Laboratory Data

All laboratory values will be listed. Laboratory measurements will also be summarized.

## 8.7.6.4 Physical Examination

All physical examination findings will be listed and any abnormality will be summarized.

## 8.7.6.5 Vital Signs

All vital sign assessment findings will be listed and summarized.

[figure not shown]
### 8.7.6.6 ECG Examination

All ECG examination findings will be listed and any abnormality will be summarized.

## 8.7.6.7 AML or MDS relapse rate by Day-100

AML or MDS relapse rate by Day-100 will be presented.

CONFIDENTIAL Page 85 of 108

## 9 ADVERSE EVENTS (DEFINITIONS AND REPORTING)

The Investigator is responsible for the detection and documentation of events meeting the criteria and definition of an AE or SAE, as provided in this protocol. During the study when there is a safety evaluation, the Investigator or site staff will be responsible for detecting, documenting, and reporting AEs and SAEs as detailed in this section of the protocol.

#### 9.1 ADVERSE EVENT

An adverse event (AE) is defined as any unfavorable or unintended sign, symptom, or disease that occurs or is reported by the subject to have occurred, or a worsening of a pre-existing condition. An AE may or may not be related to the study treatment.

AEs will be elicited through direct questioning and subject reports. Any abnormalities in visit evaluations, physical examination findings or laboratory results that the Investigator believes are clinically significant to the research subject and that occurred after initiation of the first study treatment will be reported as AEs. Abnormal findings that are NOT clinically significant should not be recorded as an AE.

